4. OUTCOMES MEASURE

- 4.1. Primary Outcomes these measures will be taken at week 0 (pre) and week 7 (post)
 - Healthspan, as assessed via a digital score within the application software.
 - **Biological Age**, as assessed via an algorithm sourced within the application.
 - Lifestyle Risk Factors, as assessed via questionnaires within the application.
 - Energy and Vitality, as assessed via questionnaires within the application.
 - Strength and Endurance, as assessed by performance measures including a timed mile walk/run, push-ups to exhaustion, and chair get-ups to exhaustion.
 - Body Composition, as assessed via a previously validated digital scale.
 - Blood Pressure, as assessed via an electronic blood pressure cuff.
 - Lifestyle Habits, as assessed by specific interfaces within the application and guided by an AI "coach."
 - **Daily Steps**, as collected via the Apple Health or Google Fit application on the subject's pre-existing personal device.

4.2. Secondary Outcomes – these measures will be taken at week 0 (pre) and week 7 (post)

- **Depression**, as assessed by the previously validated PHQ-9 subjective questionnaire.
- Quality of Life, as assessed by the previously validated SF-36 subjective questionnaire.

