5. INVESTIGATIONAL PLAN

5.1. Overall Study Design and Plan

This is a non-blinded randomized controlled pilot trial conducted over up to 8 weeks. Week 0 will involve baseline measurements and enrollment, Weeks 1-6 constitute the intervention, and Week 7 to 8 is reserved for post-testing. The study will enroll up to 200 participants, with a minimum of 50 participants who meet the inclusion criteria, and a minimum target of 20 participants completing the study in each group (experimental and control).

Participants will be recruited from across the United States using a decentralized electronic database. The study will include individuals aged 21-60 with a BMI \geq 25 (overweight) and \leq 35. Additionally, qualified subjects must have current daily activity records that show an average daily step count under 5,000. Participants must also be free of disease and must own either a personal smartphone device with the Apple Health or Google Fit application. Finally, participants must be willing to keep their device with them at all times to ensure accurate activity tracking.

Following baseline testing and enrollment in the study, participants will be randomly assigned to either the control (CON) or experimental (PRO) group. The control group will receive subject-facing materials depicting current general activity recommendations as published by the American Heart Association (AHA) and current dietary guidelines provided by the United States Department of Agriculture (USDA). The experimental group will be enrolled in the Prime Health Technologies software (Pro2col), which provides a digital diagnostic score to calculate healthspan and biological age, along with AI and group community-based coaching dynamics. Subjects will be assigned a 6 week progressive protocol targeting improvements in daily activity levels, nutritional awareness, and overall lifestyle risk factors. Both groups will then be monitored by study staff throughout the duration of the intervention period with post-testing taking place following the last week of the experiment.

Due to the remote nature of subject recruitment, no in-person facility visits are required for participants.

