5.2.1 Inclusion Criteria

- Male or female, aged 21-60 years.
- A BMI categorized as overweight (≥ 25) but not stage II obesity (≤ 35)
- Daily steps < 5,000.

- Ownership of a smartphone device with either the Apple Health or Google Fit application.
- Willingness to carry their phone in their pocket or on their person at all times to track steps during study.
- Willing to download the Pro2col application and connect it with either the Apple Health or Google Fit application.
- Willingness to complete physical tasks including a timed one-mile walk/run, regular or modified push-ups to exhaustion, and chair get-ups to exhaustion.
- For the experimental group, subjects must be willing to follow the application protocol which is laid out later in this document.
- Able to read, understand, sign and date the informed consent document (English only)
- Able and willing to comply with the scheduled visit(s) and study requirements.

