6.2. Identity of Experimental Condition

The Experimental Condition involves the use of a novel smartphone application. This application provides a digital diagnostic score to calculate healthspan and biological age, along with AI and group community-based coaching dynamics. Subjects will be assigned a 4-6-week (28-42 days depending on subject availability for last testing day) progressive protocol designed to implement lifestyle changes and solidify adherable practices including the following:

- Daily practice of intermittent fasting, eating within a time restricted eating window ranging from 8 to 12 hours.
- Increased daily steps.
- Increased awareness of hydration practices.
- Journaling
- Adherence to a lower carbohydrate, higher-protein diet.
- Improved exercise habits.
- Stress management
- Sleep habits
- Improved lifestyle risk factors, like smoking and alcohol intake

The above factors are individualized based on subject responses to questionnaires within the application. An AI-based coach and application algorithms will then send users push notifications to improve adherence to their new lifestyle factors as well as provide feedback for their logged data entries. Specifically, the application users will be required to connect the Pro2col application with either the Apple Health or Google Fit application so that necessary data can be transmitted between these applications without user input. The application creates a personalized protocol by using responses from the embedded health questionnaire to establish baseline figures that the user will improve upon. For example, if a user reports walking between 4,001-5,000 steps daily, their program will start them at 4,000 steps in week 1, gradually increasing each week until they reach the program's goal (e.g., 10,000 steps). Below are the key elements used to generate an individualized protocol, with specific goals for this user:

Steps Goal: 10,000 Steps

Incremental Approach: Starting from the user's baseline, steps will gradually increase each week to reach the target of 10,000 steps over a 4-6-week period (28-42 days depending on subject availability for the last testing day).

Example:

Week 1: Starting at the baseline (e.g., 4,000 steps)

Week 2: 5,200 steps

Week 3: 6,400 steps

Week 4: 7,600 steps

Week 5: 8,800 steps

Week 6: 10,000 steps

Calorie Goal: Moderate Fat Loss

Caloric intake will be reduced on average by 250 calories from basal calorie needs.

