APPENDIX 1. METHODOLOGIES FOR STUDY OUTCOMES.

Healthspan

A subject's healthspan will be calculated using a proprietary algorithm housed within the prime health application. Briefly, subjects will answer a number of questions regarding their daily health habits, activities, and attitudes. These data will then be placed into a mathematical equation that uses data and statistics from numerous published studies regarding longevity and mortality risk. The outcome number is a subject's estimated "Healthspan," which describes their remaining healthy and active years of life. Importantly, this number can increase or decrease based on a subject's reported lifestyle changes at the end of the intervention period.

Biological Age

The subject's biological age will be estimated using the same proprietary formula used to estimate Healthspan. Briefly, biological age is different from chronological age, which simply reflects the number of years an individual has spent on Earth. Biological age, on the other hand, takes healthy lifestyle factors into account that may prematurely age individuals past their chronological age. Conversely, active and healthy users may find that their biological age is lower than their chronological age. Importantly, this number can increase or decrease based on a subject's reported lifestyle changes at the end of the intervention period.

Lifestyle Risk Factors

These risk factors are assessed by a number of questions pertaining to lifestyle habits that the subject must answer when enrolling in the application. As also extracted from the questionnaire.

Energy and Vitality

These outcome measures are subjective reports based on subject responses to specific questions within the application's questionnaires.

Strength and Endurance

Application users will be required to perform three objective performance tests to get accurate estimates of their healthspan and biological age. These performance tests include: *Upper Body Strength*: Upper body strength will be assessed using the push-ups to failure protocol. Users will be instructed via the application on correct form and technique for push-ups specific to their gender. They will then perform as many push-ups as possible before reaching concentric muscle failure. This number will be reported to assess their upper body strength.

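### Pro2col is both the treatment and the instrument for five of nine primary outcomes; the protocol does not separate these roles for controls, and Lifestyle Habits has no measure common to both arms

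*Combined protocol and SAP*

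**What the plan says.** **The app as treatment.** Section 5.1 places randomisation after baseline testing and then states: "The experimental group will be enrolled in the Prime Health Technologies software (Pro2col"). Section 6.2 describes the condition: "This application provides a digital diagnostic score to calculate healthspan and biological age, along with AI and group community-based coaching dynamics". It adds: "The application creates a personalized protocol by using responses from the embedded health questionnaire", and "An AI-based coach and application algorithms will then send users push notifications to improve adherence to their new lifestyle factors".

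**The app as instrument.** Section 4.1 lists nine primary outcomes, measured at week 0 and week 7. One is "Lifestyle Habits, as assessed by specific interfaces within the application and guided by an AI", and the sentence ends by naming a coach. Appendix 1 has no entry for this outcome. For Lifestyle Risk Factors, Appendix 1 refers to "a number of questions pertaining to lifestyle habits that the subject must answer when enrolling in the application".

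**Who uses it.** Section 5.2.1 requires, without limiting it to an arm: "Willing to download the Pro2col application and connect it with either the Apple Health or Google Fit application". A separate criterion is limited: "For the experimental group, subjects must be willing to follow the application protocol". Sections 7.2 and 7.4 have subjects in general complete questionnaires and the healthspan and biological age calculations. Section 6.3 gives controls American Heart Association and USDA materials and does not mention the app. Section 7.3 says controls are monitored but receive no instruction on activity or nutrition. The same section ends by making the AI coach responsible for instructing and giving feedback to everyone who uses the application.

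**The concern.** When one piece of software both delivers the treatment and records the outcome, the control arm needs a stated way to be measured without being treated. Without it, two things can go wrong. Controls who open the app to be measured may also meet the coach, the notifications or a personalised programme, and the contrast between arms shrinks. Or controls may be measured by a different route from the experimental arm, and a difference between arms then mixes treatment with method of measurement. An outcome whose definition includes the coach raises the second problem directly, because coaching is part of what is being randomised.

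**Working it through.** The plan gives no figure on this point, so the check is a count followed by a comparison of sections.

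**Step 1. Count the instruments named in section 4.1.**

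| Primary outcome | Instrument in 4.1 | In the app? |
|---|---|---|
| Healthspan | digital score in the application | yes |
| Biological Age | algorithm in the application | yes |
| Lifestyle Risk Factors | application questionnaires | yes |
| Energy and Vitality | application questionnaires | yes |
| Lifestyle Habits | application interfaces, coach-guided | yes |
| Strength and Endurance | performance tests | no |
| Body Composition | digital scale | no |
| Blood Pressure | electronic cuff | no |
| Daily Steps | Apple Health or Google Fit | no |

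That is 5 in the app and 4 outside it, 5 + 4 = 9.

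**Step 2. Do controls have the app?** The download criterion in 5.2.1 applies to all, and 7.2 and 7.4 have all subjects complete the scores. Section 7.4 also tells subjects, without naming an arm, to delete the application at the end. Section 3.3 speaks of study subjects as enrolled in the application. Against this, 5.1 mentions enrolment in the software only for the experimental group, and 6.3 says nothing. On balance, all subjects have the app, and only the experimental arm must follow its programme.

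**Step 3. On that reading, is treatment switched off for controls?** No section says so. Section 6.2 ties the questionnaire answers to the personalised programme and sends notifications to users. Section 7.3 gives coaching to application users as a whole. Controls who installed the app are users in the ordinary sense, yet the same section wants them uninstructed. The two statements in 7.3 agree only if users there means the experimental arm, which the text does not say.

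**Step 4. Can each app outcome be obtained in the same way in both arms?**
- Healthspan, Biological Age, and Energy and Vitality: yes, if controls complete the same in-app questions and tests. The protocol needs to state this.
- Lifestyle Risk Factors: probably yes, because 4.1 fixes both time points. But Appendix 1 ties the questions to enrolling in the application, which 5.1 describes only for the experimental group and only after randomisation.
- Lifestyle Habits: no. Its definition includes coach guidance, controls are not to be coached, and Appendix 1 supplies no other method. The questionnaires in 7.2 and 7.4 cover activity, nutrition and lifestyle factors, but 4.1 does not name them for this outcome.

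**The case against.** The strongest reply is that the protocol already separates measurement from treatment: 5.2.1 asks everyone to download the app and only the experimental group to follow its programme. Section 6.2 describes the experimental condition, so its users are naturally that arm. The coaching sentence in 7.3 follows two sentences about the experimental group. The enrolment wording in 5.1 and Appendix 1 looks like loose usage. Most of this stands, and it is why the all-subjects reading is adopted above. It does not supply a statement of what controls can reach inside the app, and it does not give Lifestyle Habits a coach-free definition.

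A reader might infer several stronger claims that the documents do not support:
- **Controls will be coached, with a calculable loss of power.** The documents give no exposure share. Section 10.1 ties its effect size of 0.8 to habits such as daily steps, not to the app scores. Any power figure would rest on an invented share and a borrowed effect size.
- **All nine primary outcomes depend on the app.** Appendix 1 does route steps and blood pressure through it, adds an app estimate of body composition and gives push-up instruction there. But 4.1 names a non-app instrument for each of these four, and nothing makes them differ by arm for this reason.
- **Controls cannot be measured.** The download criterion and sections 7.2 and 7.4 point the other way.
- **The damage could not be repaired after data collection.** The 7.2 and 7.4 questionnaires may already provide a common measure of habits.

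**Conclusion.** The point holds as a gap in definition. Five of nine primary outcomes are taken inside the treatment software with no stated limit on controls' access. One of the five, Lifestyle Habits, cannot be obtained in the same way in both arms as defined. A second, Lifestyle Risk Factors, needs its timing and arms stated. Whether contamination would occur, and how much, is unknown.

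The conclusion assumes that all subjects install the app. If controls do not, the problem is larger, because the five outcomes would then have no stated control-arm instrument. The exploratory pilot design does not remove it, since section 10.3.1 tests all outcomes for significance.

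This should be fixed before enrolment. Whether baseline testing precedes disclosure of the assignment (5.1 against 7.1 and 7.2) is a separate point, and nothing here relies on it.

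**What to change.** 1. In 5.1 and 6.3, state that controls use Pro2col for outcome capture only, with the AI coach, push notifications, personalised protocol, community and points inactive.
2. In 7.3, limit the sentence on the AI coach to experimental-group subjects.
3. In 4.1, define Lifestyle Habits by one questionnaire given identically to both arms at baseline and post-test, without coach guidance. The 7.2 and 7.4 questionnaires already cover the content and could be named.
4. In Appendix 1, add that method for Lifestyle Habits, and state that the Lifestyle Risk Factors questions are answered at baseline and post-test in both arms.

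The cost is a protocol amendment and some app configuration, with no extra subjects or visits. The documents do not say whether the app supports a capture-only setting. If it does not, use the identical 7.2 and 7.4 questionnaires and Apple Health or Google Fit step data as the between-arm measures, and do not treat the in-app scores as between-arm primary outcomes. Healthspan and Biological Age would then be lost as randomised comparisons, because Appendix 1 describes a proprietary algorithm housed in the app and nothing indicates that it can be run elsewhere.

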5. INVESTIGATIONAL PLAN

5.1. Overall Study Design and Plan

This is a non-blinded randomized controlled pilot trial conducted over up to 8 weeks. Week 0 will involve baseline measurements and enrollment, Weeks 1-6 constitute the intervention, and Week 7 to 8 is reserved for post-testing. The study will enroll up to 200 participants, with a minimum of 50 participants who meet the inclusion criteria, and a minimum target of 20 participants completing the study in each group (experimental and control).

Participants will be recruited from across the United States using a decentralized electronic database. The study will include individuals aged 21-60 with a BMI \geq 25 (overweight) and \leq 35. Additionally, qualified subjects must have current daily activity records that show an average daily step count under 5,000. Participants must also be free of disease and must own either a personal smartphone device with the Apple Health or Google Fit application. Finally, participants must be willing to keep their device with them at all times to ensure accurate activity tracking.

Following baseline testing and enrollment in the study, participants will be randomly assigned to either the control (CON) or experimental (PRO) group. The control group will receive subject-facing materials depicting current general activity recommendations as published by the American Heart Association (AHA) and current dietary guidelines provided by the United States Department of Agriculture (USDA). The experimental group will be enrolled in the Prime Health Technologies software (Pro2col), which provides a digital diagnostic score to calculate healthspan and biological age, along with AI and group community-based coaching dynamics. Subjects will be assigned a 6 week progressive protocol targeting improvements in daily activity levels, nutritional awareness, and overall lifestyle risk factors. Both groups will then be monitored by study staff throughout the duration of the intervention period with post-testing taking place following the last week of the experiment.

Due to the remote nature of subject recruitment, no in-person facility visits are required for participants.

5.2. Selection of Study Population

The following eligibility criteria are designed to select subjects for whom protocol requirements are considered appropriate. All relevant medical and non-medical conditions should be taken into consideration when deciding whether this protocol is suitable for a particular subject.

5.2.1 Inclusion Criteria

- Male or female, aged 21-60 years.
- A BMI categorized as overweight (≥ 25) but not stage II obesity (≤ 35)
- Daily steps < 5,000.

- Ownership of a smartphone device with either the Apple Health or Google Fit application.
- Willingness to carry their phone in their pocket or on their person at all times to track steps during study.
- Willing to download the Pro2col application and connect it with either the Apple Health or Google Fit application.
- Willingness to complete physical tasks including a timed one-mile walk/run, regular or modified push-ups to exhaustion, and chair get-ups to exhaustion.
- For the experimental group, subjects must be willing to follow the application protocol which is laid out later in this document.
- Able to read, understand, sign and date the informed consent document (English only)
- Able and willing to comply with the scheduled visit(s) and study requirements.

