5.2.2 Exclusion Criteria

Subjects presenting any of the following will not be included in the study:

- Currently taking (within the past 30 days) ergogenic dietary supplements including, creatine, protein, amino acids, or stimulants other than caffeine (yohimbe, ephedrine, etc.)
- Currently taking performance enhancing drugs (testosterone or other anabolic-androgenic steroids), human growth hormone, insulin, etc.
- History or current malignancy
- Receiving chemotherapy agents or radiation treatments
- Musculoskeletal disease (muscular dystrophy, arthritis, etc.)
- Recent (<3-months) musculoskeletal injuries
- BMI < 25 or > 35 kg/m²
- Diagnosis of a terminal illness
- Use of prescription medications that influence body composition (i.e., prescription hormone therapies, etc.)
- History of alcohol abuse
- History or current drug abuse
- History or current diagnosis of depression.
- History or current diagnosis of suicidal thoughts/ideation.
- A score of \geq 10 arbitrary units on the PHQ-9 during baseline testing.
- History or current cigarette smoke (including vaping) within the past 14 days from the screening visit
- Insulin-dependent diabetes and/or metformin use
- Chronic kidney or liver disease
- Has significant concurrent illnesses (controlled or uncontrolled), such as diabetes, lupus, epilepsy, or cardiac disorders, hepatitis B/C, HIV, serious mental health illness such as dementia or schizophrenia; psychiatric hospitalization in the past two years,

or other, which in the opinion of the investigator, such conditions might be aggravated as a result of treatment

- The investigator feels that for any reason the subject is not eligible to participate in the study
- History of uncontrolled cardiovascular disease (i.e., myocardial infarction, hypertension, hypercholesterolemia, peripheral vascular disease, other)
- Developmental disability or cognitive impairment that would preclude adequate comprehension of the informed consent form and/or ability to follow study subject requirement and/or record the necessary study measurements
- A family member of the investigator or an employee of the investigator
- Participation in any other investigational study within 30 days prior to consent.

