7.1. SCREENING

Subjects who signed the informed consent form will have the following assessments performed:

- Inclusion and exclusion criteria
- Medical and medication history
- Demographic and baseline characteristics

Subjects who meet all required entry criteria will be enrolled in the study and will be assigned a subject No./ID in the 100 series starting with "101" and continuing in sequential order until enrollment is met.

Enrolled subjects will be scheduled for a remote consultation with a member of the study staff to go over the details of the study, their condition assignment, and all related materials and procedures for the study.

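### No specific eligibility criterion or listed screening item addresses pregnancy, planned pregnancy or breastfeeding, although the experimental arm restricts diet and pregnancy can change two primary outcomes

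*Combined protocol and SAP*

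**What the plan says.** Section 5.2.1 admits "Male or female, aged 21-60 years" and attaches no condition about pregnancy or breastfeeding. Section 5.2.2 lists 23 exclusions, and none names either state. Those nearest to the subject are a drug exclusion, "Use of prescription medications that influence body composition (i.e., prescription hormone therapies, etc", the weight limits, "BMI < 25 or > 35 kg/m²", and a catch-all, "The investigator feels that for any reason the subject is not eligible to participate in the study".

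Two general statements also bear on entry. Section 5.1 says "Participants must also be free of disease", and 5.2 says "All relevant medical and non-medical conditions should be taken into consideration when deciding whether this protocol is suitable for a particular subject". Screening in 7.1 consists of the criteria check, "Medical and medication history", and demographic and baseline characteristics. Section 8.1 describes the history as a check on whether participation is appropriate, but gives no questions for any condition. Section 5.1 makes the trial remote, with no required in-person visits.

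The experimental programme in 6.2 includes daily time-restricted eating, a lower-carbohydrate and higher-protein diet, and a calorie goal: "Caloric intake will be reduced on average by 250 calories from basal calorie needs". Under 7.2 and 7.4, both arms do push-ups and chair get-ups to exhaustion and a timed mile. Section 6.5 lists fainting and dizziness under fitness programmes, fasting and low-carbohydrate diets. Body composition and blood pressure are primary outcomes in 4.1, and Appendix 1 specifies bioelectrical impedance for the former.

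**The concern.** The criteria deal in detail with foreseeable influences on the outcomes and on safety, such as creatine, metformin, recent smoking or vaping, and hormone prescriptions. They are silent on one that is common in women across much of the eligible age range. The drug exclusion shows that the sponsor regards outside influences on body composition as grounds for keeping someone out, and pregnancy is an influence of the same kind.

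Two things are at stake. The first is subject protection: a woman who is pregnant or breastfeeding could be randomised to dietary restriction without anyone having been required to ask. The second is measurement. Body composition and blood pressure are taken before and after the intervention, and a change driven by pregnancy would be recorded as part of an arm's response. Section 10.3.1 has no rule for such data.

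**Working it through.** The plan gives no figure on this point, so there is nothing to reproduce. The check has two parts: whether any text closes the gap, and how far one subject could move a result.

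**Text that might keep such a subject out**

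| Text | Section | Does it reach pregnancy or breastfeeding? |
|---|---|---|
| Absence of disease | 5.1 | No. Neither state is a disease. |
| BMI limits | 5.2.2 | No. They do not separate pregnancy weight from other weight. |
| Drugs influencing body composition | 5.2.2 | No. It concerns prescriptions. |
| General suitability sentence | 5.2 | Possibly, by judgement. No rule is named. |
| Investigator catch-all | 5.2.2 | Possibly, by judgement, if the investigator knows. |
| Medical and medication history | 7.1, 8.1 | Possibly. Its questions are not specified. |

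Sections 6.5 (risks), 7.5 (withdrawal) and 9 (adverse events) do not mention pregnancy either. The last three rows can catch a case, but none requires the question to be asked.

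**Who is exposed to what**

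- Dietary restriction (6.2): experimental arm only.
- Tests to exhaustion (7.2, 7.4): both arms, as assessments before and after the intervention.

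**Influence of one subject on the between-arm difference**

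Inputs from 5.1 are a minimum target of 20 completers per arm and a maximum enrolment of 200. Assuming equal allocation and full completion, the maximum gives 200 / 2 = 100 per arm.

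Let D be the gap between her change and the change she would otherwise have had, SD the standard deviation of change, and n the completers per arm.

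- Shift in her arm's mean, and so in the difference between arms: D / n. This is D / 20 = 0.05 D at the minimum and D / 100 = 0.01 D at the maximum.
- Standard error of the difference: SD × √(2/n).
- Shift in standard errors: (D / n) / (SD × √(2/n)) = (D / SD) / √(2n), with √40 = 6.32 and √200 = 14.14.

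The documents give neither D nor SD, so D / SD is assumed to lie between 1 and 3:

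| Assumed D / SD | n = 20 per arm | n = 100 per arm |
|---|---|---|
| 1 | 1 / 6.32 = 0.16 SE | 1 / 14.14 = 0.07 SE |
| 2 | 2 / 6.32 = 0.32 SE | 2 / 14.14 = 0.14 SE |
| 3 | 3 / 6.32 = 0.47 SE | 3 / 14.14 = 0.21 SE |

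On these assumptions one subject moves the result by less than half a standard error even at the smallest planned size. Her outlying value would also widen the observed SD, which lowers the ratio further.

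**Direction**

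A woman pregnant at entry is as likely to fall in one arm as in the other under equal allocation. Over repeated randomisations the shifts cancel in expectation, and what remains is extra variance.

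**The case against.** The strongest reply is that the plan already has ways to keep such a subject out. The catch-all in 5.2.2 allows exclusion for any reason, 5.2 tells staff to weigh all relevant conditions, and 7.1 requires a medical history and schedules a remote consultation. Pregnancy is a normal item in a medical history, and the protocol does not list the history questions for any other condition. This stands in part. A reader might infer that pregnant women satisfy every criterion, or that nobody would ask, and the documents support neither. They support only the statement that no specific criterion and no listed item covers the matter. The consent pages were also removed from the text available here, so any wording there cannot be checked.

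Three further limits stand:

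- The exhaustion tests are assessments in both arms, not part of the intervention.
- Bodyweight is recorded (7.2) but is not named as a primary outcome in 4.1, so a calculation on weight alone does not describe a primary endpoint.
- The 250-calorie figure in 6.2 sits among goals for an example user in an individualised programme and is taken from basal needs. It cannot serve as the arm's average deficit below maintenance.

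What does not stand is that discretion closes the gap. Discretion depends on knowing the fact, and in a remote trial nothing written requires that it be asked.

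**Conclusion.** The point holds as an omission. The plan can be followed as written and still randomise a pregnant or breastfeeding woman to dietary restriction, and two primary outcomes can then change for reasons unrelated to the app.

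The effect on the results is modest and cannot be stated as a percentage. It depends on how many such women volunteer, possibly none, and on a size of change that the documents do not give. A reader might infer a systematic bias against or in favour of the app. The documents do not support that, because allocation is random and pregnancy at entry is balanced in expectation; the main consequence is noise. The case for change therefore rests on subject protection and on consistency with the existing drug exclusion at least as much as on precision.

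Two assumptions are used. That pregnancy alters impedance readings and blood pressure is general physiology, not a statement in the documents. That the removed pages contain no overriding rule cannot be confirmed, although the lists in 5.2.1 and 5.2.2 appear complete.

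**What to change.** - **5.2.2:** add exclusions for self-reported pregnancy, pregnancy planned during the study, and breastfeeding.
- **7.1:** list these as questions in the history.
- **10.3.1:** state that body composition and blood pressure data collected after a pregnancy reported mid-study are flagged, and that a sensitivity analysis omits them.

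Whether to test for pregnancy, and how a pregnancy arising during the study is managed clinically, are for the sponsor and IRB to decide and write down. The documents give no basis for settling either here.

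The cost is a few lines of text, added screening questions and one sensitivity analysis that may have nothing to omit. The downside is a small loss of eligible subjects.
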